3.2 Exclusion Criteria

___ 1. Inability to swallow tablets.

___ 2. Previously identified allergy or hypersensitivity to components of the study treatment formulation or dacarbazine.

___ 3. Subjects with a prior or concurrent malignancy whose natural history or treatment does have the potential to interfere with the safety or efficacy assessment of the investigational regimen are ineligible for this trial.

Patient MRN (COH Only)	Patient Initials (F, M, L):
Institution:	

___4. Pregnant or lactating females. Pregnant women are excluded from this study because cabozantinib and temozolomide are antineoplastic agents with potential for teratogenic or abortifacient effects. Because there is an unknown but potential risk for adverse events in nursing infants secondary to treatment of the mother with cabozantinib and temozolomide, breastfeeding should be discontinued if the mother is treated with cabozantinib and temozolomide.

___5. Prior treatment with cabozantinib or temozolomide.

___6. Receipt of any of the following:

- Any type of small molecule kinase inhibitor (including investigational kinase inhibitor) within 14 days before first dose of study treatment.
- Any type of cytotoxic, biologic or other systemic anticancer therapy (including investigational) within 28 days before first dose of study treatment (excluding drugs in 3.2.4).
- Radiation therapy for bone metastasis within 14 days before first dose of study treatment,
- Any other radiation therapy within 28 days before first dose of study treatment.
- Systemic treatment with radionuclides within 42 days before the first dose of study treatment.

Note: Subjects with clinically relevant ongoing complications from prior radiation therapy are not eligible.

- Major surgery (e.g., laparoscopic nephrectomy, GI surgery, removal or biopsy of brain metastasis) within 2 weeks before first dose of study treatment. Minor surgeries within 10 days before first dose of study treatment. Subjects must have complete wound healing from major surgery or minor surgery before first dose of study treatment. Subjects with clinically relevant ongoing complications from prior surgery are not eligible.

Patient MRN (COH Only)	Patient Initials (F, M, L):
Institution:	

- ___7. Corrected QT interval calculated by the Bazetts formula (QTcF) >500 ms per electrocardiogram (ECG) within 28 days before first dose of study treatment.
- *Note: If a single ECG shows a QTcF with an absolute value >500 ms, two additional ECGs at intervals of approximately 3 min must be performed within 30 min after the initial ECG, and the average of these three consecutive results for QTcF will be used to determine eligibility.*
- ___8. The subject has uncontrolled, significant intercurrent or recent illness including, but not limited to, the following conditions:
- a. Cardiovascular disorders:
 - Subjects with known history or current symptoms of cardiac disease, or history of treatment with cardiotoxic agents, should have a clinical risk assessment of cardiac function using the New York Heart Association Functional Classification. To be eligible for this trial, subjects should be class 2B or better.
 - Uncontrolled hypertension defined as sustained blood pressure (BP) > 140 mm Hg systolic or > 90 mm Hg diastolic despite optimal antihypertensive treatment.
 - Stroke (including transient ischemic attack [TIA]), myocardial infarction (MI), or other ischemic event within 6 months before the first dose.
 - Subjects with a diagnosis of incidental, subsegmental PE or DVT within 6 months are allowed if stable, asymptomatic, and treated with a stable dose of permitted anticoagulation (see exclusion criterion #9) for at least 1 week before first dose of study treatment.
 - b. Gastrointestinal (GI) disorders including those associated with a high risk of perforation or fistula formation:
 - The subject has evidence of tumor invading the GI tract, active peptic ulcer disease, inflammatory bowel disease (e.g., Crohn's disease), diverticulitis, cholecystitis, symptomatic cholangitis -

Patient MRN (COH Only)	Patient Initials (F, M, L):
Institution:	

or appendicitis, acute pancreatitis, acute obstruction of the pancreatic duct or common bile duct, or gastric outlet obstruction.

- Abdominal fistula, GI perforation, bowel obstruction, or intra-abdominal abscess within 6 months before the first dose.

Note: Complete healing of an intra-abdominal abscess must be confirmed before the first dose.

- c. Clinically significant hematuria, hematemesis, or hemoptysis of > 0.5 teaspoon (2.5 ml) of red blood, or other history of significant bleeding (e.g., pulmonary hemorrhage) within 84 days before the first dose.
- d. Cavitating pulmonary lesion(s) or known endotracheal or endobronchial disease manifestation.
- e. Lesions invading or encasing any major blood vessels.
- f. Other clinically significant disorders that would preclude safe study participation.
 - Serious non-healing wound/ulcer/bone fracture.
 - Uncompensated/symptomatic hypothyroidism.
 - Moderate to severe hepatic impairment (Child-Pugh B or C).

___9. Concomitant anticoagulation with oral anticoagulants (e.g., warfarin, direct thrombin and factor Xa inhibitors) or platelet inhibitors (e.g., clopidogrel). Washout period is considered to be 5 half-lives of the drug. Allowed anticoagulants are the following :

- a. Low-dose aspirin for cardio protection (per local applicable guidelines) is permitted.
- b. Low-dose low molecular weight heparins (LMWH) are permitted.
- c. Anticoagulation with therapeutic doses of LMWH or with direct factor Xa inhibitors rivaroxaban, edoxaban, or apixaban is allowed in subjects without known brain metastases who are on a stable dose of the anticoagulant for at least 1 week before first dose of study –

Patient MRN (COH Only)	Patient Initials (F, M, L):
Institution:	

treatment without clinically significant hemorrhagic complications from the anticoagulation regimen or the tumor.

Eligibility Confirmed* by (Choose as applicable):	Print Name	Signature	Date
 Site PI			
 Authorized study MD			
 Study Nurse			
 Study CRA/ CRC			
 Other: _____			

*Eligibility should be confirmed per institutional policies.

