3.0 SUBJECT ELIGIBILITY

The target population for this phase II study is subjects with unresectable or metastatic uterine and non-uterine leiomyosarcoma and other types of soft tissue sarcoma (non-leiomyosarcoma). This will be a multicenter trial conducted with City of Hope National Medical Center serving as the lead site and coordinating center for this study.

Participating sites will include the University of Iowa, Washington University, University of Wisconsin and Northwestern University.

Eligibility will be evaluated by the study team according to the following criteria.

Eligibility waivers are not permitted. Subjects must meet all of the inclusion and none of the exclusion criteria to be registered to the study. Study treatment may not begin until a subject is registered. Please refer to [Section 11](#) for complete instructions regarding registration procedures.

Patient MRN (COH Only)	Patient Initials (F, M, L):
Institution:	

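### Exclusion 6 exempts drugs by pointing to the pregnancy criterion, so anticancer kinase inhibitors fall under both a 14-day and a 28-day washout; the synopsis's 6-week BCNU/mitomycin C washout is missing from Section 3

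*Combined protocol and SAP*

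**What the plan says.** Exclusion 6 in Section 3.2 lists washout periods. The first bullet covers "Any type of small molecule kinase inhibitor (including investigational kinase inhibitor) within 14 days before first dose of study treatment". The second covers cytotoxic, biologic or "other systemic anticancer therapy (including investigational) within 28 days before first dose of study treatment (excluding drugs in 3.2.4"). Later bullets set 14 days for radiation to bone metastases, then "Any other radiation therapy within 28 days before first dose of study treatment", then "Systemic treatment with radionuclides within 42 days before the first dose of study treatment".

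Section 3.2 has no numbered subsection 3.2.4. Its item 4 begins "Pregnant or lactating females" and mentions only cabozantinib and temozolomide. Item 5 excludes "Prior treatment with cabozantinib or temozolomide" with no time limit.

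Section 3.0 states "Eligibility waivers are not permitted" and "Subjects must meet all of the inclusion and none of the exclusion criteria to be registered to the study". Section 11.4 makes the signed checklist, printed from Section 3.0, part of the registration packet.

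The Study Summary, under key eligibility, asks for at least 4 weeks since cytotoxic therapy and at least 6 weeks since BCNU or mitomycin C. It then sends the reader to Section 3.0 for the complete criteria.

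**The concern.** There are two separate defects. They act in opposite directions, and nothing in the documents links them.

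**The pointer.** The 28-day bullet was meant to exempt some drugs, but the reference leads to a criterion that lists no prior therapy. If the exemption is empty, a kinase inhibitor given for cancer is caught by both bullets. A site then has two poor options. It can apply the text and delay or turn away a subject whom the protocol evidently meant to admit. Or it can apply the apparent intent and register a subject who is ineligible on the text, with no waiver available. The case can arise here: inclusion 4 allows up to five prior chemotherapy regimens and leaves the definition of a regimen to the investigator, and Sections 1.2.5 and 1.4 discuss pazopanib and sorafenib in sarcoma.

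**The missing washout.** The checklist lacks a rule that the synopsis states. A subject could be registered on a correctly completed checklist and still breach the synopsis.

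**Working it through.** This is a check of the text. No power or error-rate figure is involved.

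**Step 1: what the pointer exempts.** Item 4 names cabozantinib and temozolomide. Anyone previously given either is already out under item 5. The number of otherwise eligible subjects freed by the exemption is therefore zero.

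**Step 2: which bullets apply.** A kinase inhibitor given for cancer is a small-molecule kinase inhibitor (first bullet, 14 days) and also a systemic anticancer therapy (second bullet, 28 days). Section 3.0 requires that no exclusion be met, so the longer window controls. A kinase inhibitor given for a non-cancer indication stays under the first bullet alone.

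**Step 3: what was probably intended.** Four features point to 14 days:
- The first bullet is specific to the class.
- The second bullet carries an exemption, and kinase inhibitors are the only drug class in exclusion 6 with a shorter window.
- The radiation bullets follow the same sequence of 14 days for a named case and 28 days for everything else.
- The synopsis attaches 4 weeks to cytotoxic therapy.

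**Step 4: the affected kinase-inhibitor band.** Let *d* be whole days from the last dose to the first study dose. Subjects who clear the 14-day bullet but fail the 28-day bullet are:

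| Reading of the boundary day | Condition | Days | Count |
|---|---|---|---|
| Allowed | 14 ≤ *d* < 28 | 14 to 27 | 27 − 14 + 1 = 14 |
| Excluded | 14 < *d* ≤ 28 | 15 to 28 | 28 − 15 + 1 = 14 |
| Common to both | | 15 to 27 | 27 − 15 + 1 = 13 |

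**Step 5: the BCNU/mitomycin C gap.** Sections 3.1 and 3.2 name neither drug, and the only 42-day line covers radionuclides. Under exclusion 6 both drugs fall under the 28-day bullet alone. The synopsis minimum is 6 × 7 = 42 days. Subjects who clear Section 3 but not the synopsis are:

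| Reading of day 28 | Condition | Days | Count |
|---|---|---|---|
| Allowed | 28 ≤ *d* < 42 | 28 to 41 | 41 − 28 + 1 = 14 |
| Excluded | 28 < *d* < 42 | 29 to 41 | 41 − 29 + 1 = 13 |

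**The case against.** The strongest reply is that the pointer is a typographical slip whose meaning is clear. On an ordinary specific-over-general reading the kinase-inhibitor bullet keeps its own window, and nothing in the documents shows that anyone would apply 28 days. Every registration also passes one central review by the data coordinating center (Section 11.4), so a single interpretation can be applied at all sites. Under the strict reading the cost is a wait of about two weeks at most, part of which can overlap the 28-day screening window in Section 5.0. That reading is also the more conservative one, so it adds no safety exposure.

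On the second item, Section 1.1 lists the current chemotherapy options and neither BCNU nor mitomycin C is among them, so the affected group may be empty. The 6-week rule still stands in the synopsis. Inclusion 9 (recovery from earlier toxicity) and the blood-count limits in inclusion 6 still apply.

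These points are fair and keep the matter small. They do not repair the text. The specific-over-general argument supports the intent, but the drafters evidently thought an express exemption was needed and then sent it to the wrong place. Central review limits inconsistency between sites, yet the reviewer still has to choose between the wording and the intent, with waivers ruled out. A rule found only in the synopsis is not on the form that is signed at registration.

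**Conclusion.** Both defects hold, and both are minor. As written, exclusion 6 holds a subject who took a kinase inhibitor for cancer to 28 days despite the express 14-day line. Days 15 to 27 are affected on any reading, and the full band is 14 days. Section 3 admits a subject 29 to 41 days after BCNU or mitomycin C (from day 28 if the boundary day is allowed) whom the synopsis bars.

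The conclusion on the pointer assumes that its target is item 4 of Section 3.2, the only place in that section that fits the number. That 14 days was intended is an inference from the surrounding text, though a strong one. The documents give no count of affected subjects, and none is estimated. The Simon design's sample size and error rates and the primary analysis do not change.

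**What to change.** Make two independent wording changes to exclusion 6 in the next amendment:

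1. Once the sponsor confirms the intent, replace the reference to 3.2.4 in the second bullet with: *excluding small-molecule kinase inhibitors, which are covered by the first bullet*.
2. Add a bullet: *BCNU or mitomycin C less than 6 weeks (42 days) before first dose of study treatment*. The checklist then matches the synopsis.

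The cost is two lines of checklist text, with no added procedures, visits or subjects.

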3.3 Inclusion of Women and Minorities

Both women and men and members of all races and ethnic group are eligible for this trial.

3.4 Population and Accrual Overview

The target population for this phase II study is subjects with unresectable or metastatic uterine and non-uterine leiomyosarcoma and other types of soft tissue sarcoma (non-leiomyosarcoma). This will be a multi-center study with City of Hope National Medical Center serving as the lead institution and coordinating center.

A total of 72 subjects will be enrolled including 42 of uterine and non-uterine leiomyosarcoma and up to 30 subjects in the exploratory cohort for other types of soft tissue sarcomas. Potential subjects may be referred to the Principal Investigator (PI) at City of Hope National Medical Center. Subjects at each of the participating sites may be referred to the respective local PI at each site.

4.0 TREATMENT PLAN

4.1 Overview

During the Pre Treatment Period, subjects are consented and qualified (screened) for the study. Informed consent must be obtained before initiation of any clinical screening procedure that is performed solely for the purpose of determining eligibility for this study. Evaluations performed as part of routine care before

informed consent can be considered as screening evaluations if done within the defined screening period, and if permitted by the site's institutional review board (IRB)/ethics committee (EC) policies.

Study eligibility is based on meeting all of the study inclusion criteria and none of the exclusion criteria at screening before registration and study treatment administration. The following assessments will be conducted before subjects receiving their first dose of cabozantinib/temozolomide on this protocol:

- Physical exam (Vital signs, height, weight, ECOG)
- Clinical laboratory tests (CBC with differential, CMP, amylase, lipase, GGT, LDH, Magnesium, Phosphorus, TSH, FT3, FT4, PT/INR, PTT, pregnancy test (urine or serum)).
- Urinalysis/UPCR
- EKG
- Tumor assessment (all sites of known disease)

For each subject, the Pre-Treatment Period ends upon receipt of the first dose of study treatment or final determination that the subject is ineligible for the study.

4.2 Treatment Plan

Subjects will be registered to 2 cohorts based on disease. Subjects with unresectable or metastatic uterine and non-uterine leiomyosarcoma will be registered to cohort 1 and subjects with unresectable or metastatic other soft tissue sarcomas (non-leiomyosarcoma) will be registered to cohort 2. The first 14 subjects to be enrolled in the study in either cohort will serve as a safety lead in. After the first 14 subjects complete 1 cycle, investigators will review all grade 3 and 4 toxicities and confirm safety to proceed with additional subjects. These subjects will be observed for 2 weeks following completion of cycle 1. Refer to Section 4.4 for details. A Simon stage II design will be employed in cohort 1 to determine favorable outcome. Cohort 2 is considered exploratory.

Subjects will take oral cabozantinib (40 mg starting dose) once daily for 28 days and temozolomide 150 mg/m² (Cycle 1) on Days 1-5 of each 28 day cycle. For

Cycles 2+, temozolomide should be escalated to 200 mg/m² on Days 1-5 of each 28 day cycle, if absolute ANC $\geq 1.5 \times 10^9/L$ and platelet count $\geq 100 \times 10^9/L$.

Treatment will continue until either disease progression, the occurrence of unacceptable drug-related toxicity or for other reason(s) for subject withdrawal as described in [Section 4.8](#). Subjects who are removed from the study treatment for toxicity should be followed until toxicity resolves to Grade 1 or baseline.

Subjects should be instructed to immediately inform the treating investigator of any AEs. Subjects experiencing dizziness, sleepiness, or other symptoms that could influence alertness or coordination should be advised not to drive or operate other heavy machinery.

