4.3 Treatment Administration

Agent	Dose	Route	Schedule	Cycle Length
Cabozantinib	40 mg (starting dose)	PO	QD	4 Weeks (28 days)
Temozolomide	150 mg/m ² (starting dose for Cycle 1), then 200 mg/m ² (Cycles 2+)	PO	QD Days 1-5 of each cycle	

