4.4.4 Management of Temozolomide Related Adverse Events

The most common adverse reactions ($\geq 10\%$ incidence) are: alopecia, fatigue, nausea, vomiting, headache, constipation, anorexia, convulsions, rash, hemiparesis, diarrhea, asthenia, fever, dizziness, coordination abnormal, viral infection, amnesia, and insomnia.

The most common Grade 3 to 4 hematologic laboratory abnormalities ($\geq 10\%$ incidence) that have developed during treatment with temozolomide are: lymphopenia, thrombocytopenia, neutropenia, and leukopenia.

Allergic reactions have also been reported.

Please refer to [Appendix A](#) for dose modification algorithms for potential combination treatment related adverse events.

Table 0-8: Temozolomide Dosing Interruption or Discontinuation during Treatment Period

Toxicity	Temozolomide Interruption	Temozolomide Discontinuation	Reduce Temozolomide by 1 Dose Level
Absolute Neutrophil Count (ANC)	≥ 0.5 and $< 1.5 \times 10^9/L$	$< 0.5 \times 10^9/L$	≥ 0.5 and $< 1.0 \times 10^9/L$
Platelet Count	≥ 10 and $< 100 \times 10^9/L$	$< 10 \times 10^9/L$	≥ 10 and $< 50 \times 10^9/L$
NCI-CTCAE non-hematological toxicity (except for alopecia, nausea and vomiting)	Grade 2	Grade 3 or 4	Grade 3

Treatment with temozolomide may be continued when all of the following conditions are met:

- $ANC \geq 1.5 \times 10^9/L$
- Platelet count $\geq 100 \times 10^9/L$
- NCI-CTCAE non-hematological toxicity \leq Grade 1 (except for alopecia, nausea and vomiting)

Table 0-9: Temozolomide Dose Levels

Dose 0 (Assigned Starting Dose)	Dose Level 1	Dose Level 0	Dose Level -1
150 mg/m ² /day	200 mg/m ² /day	150 mg/m ² /day	100 mg/m ² /day

Please see [Appendix B](#) for Daily Dose Calculations by Body Surface Area (BSA).

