8.2 Temodar/Temozolomide

Temodar contains temozolomide, an imidazotetrazine derivative. The chemical name of temozolomide is 3, 4-dihydro-3-methyl-4-oxoimidazo (5, 1-d) - as-tetrazine-8-carboxamide.

Each capsule for oral use contains either 5 mg, 20 mg, 100 mg, 140 mg, 180 mg, or 250 mg of temozolomide.

Only during Cycle 1, temozolomide should be taken orally at 150 mg/ m² Days 1-5 of a 28-day cycle. Thereafter, if absolute ANC $\geq 1.5 \times 10^9/L$ and platelet count $\geq 100 \times 10^9/L$, the dose should be escalated to 200 mg/m² Days 1-5 of a 28-day cycle.

Temozolomide is contraindicated in subjects who have a history of hypersensitivity reaction (such as urticarial, allergic reaction including anaphylaxis, toxic epidermal necrolysis, and Stevens-Johns syndrome) and subjects who have a history of hypersensitivity to dacarbazine.

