40. Schiff, D., et al., Phase 1 dose escalation trial of the safety and pharmacokinetics of cabozantinib concurrent with temozolomide and radiotherapy or temozolomide after radiotherapy in newly diagnosed patients with high-grade gliomas. *Cancer*, 2016. 122(4): p. 582-7.
doi:10.1097/CAD.000000000000108

APPENDIX A - DOSE MODIFICATION ALGORITHMS FOR POTENTIAL COMBINATION TREATMENT RELATED ADVERSE EVENTS

AE Terms & Descriptions	Dose Modification Algorithms
Diarrhea	
a. Grade 1-2 (duration < 48 hr)	a. Continue Cabozantinib at the current dose. If it does not improve with supportive measures consider a dose reduction. Continue temozolomide at the current dose.
b. Intolerable Grade 2 or Grade 3	b. Interrupt Cabozantinib and temozolomide until Grade ≤ 1 then consider restarting Cabozantinib at reduced dose. Dose reduce temozolomide by one dose level for Grade 3 only. Discontinue temozolomide for grade 4.
	c. Refer to the Table 0-3 for the management of diarrhea.
Neutropenia	
a. Neutrophil count <1.5	a. Interrupt temozolomide and cabozantinib until neutrophil count $\geq 1.5 \times 10^9/L$.
b. Neutrophil count <1.0	b. Interrupt temozolomide and cabozantinib until $\geq 1.5 \times 10^9/L$. Reduce temozolomide by 1 dose level. Continue cabozantinib at the same.
c. Neutrophil count <0.5	c. Discontinue temozolomide, interrupt cabozantinib until neutrophil count is $\geq 1.5 \times 10^9/L$ then resume at same dose.
Febrile Neutropenia	
Grade 3 or 4	Interrupt temozolomide and cabozantinib until resolved. Upon resumption, reduce temozolomide by 1 dose level. Continue cabozantinib at the same dose.
Thrombocytopenia	
Grade 1 or 2	Interrupt temozolomide until $\geq 100 \times 10^9/L$. Continue cabozantinib.

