APPENDIX B- DAILY DOSE CALCULATIONS BY BODY SURFACE AREA BSA

Total BSA (m²)	200 mg/m² (mg daily)	150 mg/m² (mg daily)
1.0	200	150
1.1	220	165
1.2	240	180
1.3	260	195
1.4	280	210
1.5	300	225
1.6	320	240
1.7	340	255
1.8	360	270
1.9	380	285
2.0	400	300
2.1	420	315
2.2	440	330
2.3	460	345
2.4	480	360
2.5	500	375

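### Temozolomide dosing rules conflict: Table 0-8 both stops and reduces at Grade 3 non-hematological toxicity, and the Cycle 2+ escalation has no exception for an earlier reduction trigger

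*Combined protocol and SAP*

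**What the plan says.** **Escalation.** Temozolomide starts at 150 mg/m² in Cycle 1. Section 4.2 then says: "Cycles 2+, temozolomide should be escalated to 200 mg/m² on Days 1-5 of each 28 day cycle, if absolute ANC" is at least 1.5 × 10⁹/L and platelets are at least 100 × 10⁹/L. Section 8.2 uses the same two thresholds and says "the dose should be escalated to 200 mg/m² Days 1-5 of a 28-day cycle". The regimen table in Section 4.3 prints the step with no condition: "starting dose for Cycle 1), then 200 mg/m"². The Treatment Plan entry of the Study Summary and Section 1.3 also tie the step to neutrophil and platelet counts only.

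**Reduction and discontinuation.** Table 0-8 in Section 4.4.4 has a column headed "Reduce Temozolomide by 1 Dose Level". It applies to ANC from 0.5 to below 1.0, platelets from 10 to below 50, and Grade 3 in the row "NCI-CTCAE non-hematological toxicity (except for alopecia, nausea and vomiting"). In that same row the discontinuation column reads Grade 3 or 4.

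Appendix A reduces temozolomide by one level at Grade 3 and discontinues it at Grade 4, both for diarrhea and for other temozolomide-related events. For neutrophils below 1.0 it holds treatment until recovery to 1.5 and then says: "Reduce temozolomide by 1 dose level. Continue cabozantinib at the same" dose. It has similar entries for febrile neutropenia and for Grade 3 or 4 thrombocytopenia.

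**Resumption.** Section 4.4.4 adds: "Treatment with temozolomide may be continued when all of the following conditions are met". The conditions are ANC at least 1.5, platelets at least 100, and non-hematological toxicity no worse than Grade 1 (same exceptions).

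**The concern.** A dosing rule should give one answer for one subject. Here two sets of instructions can give two.

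For Grade 3 non-hematological toxicity, the reader of Table 0-8 is told both to stop temozolomide and to continue it one level lower. That decides whether the subject stays on half of the combination.

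For escalation, the stated test looks only at counts and does not ask what happened in the previous cycle. A subject who has just met a reduction trigger and recovered could, on the letter of Section 4.2, go up a level when the toxicity rules send the subject down. Section 1.3 says the Cycle 1 dose was modified because of observed toxicity, and Section 4.4 acknowledges limited clinical experience with the combination. In a multicenter trial, which instruction wins should not be left to each site.

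**Working it through.** **Part 1: Grade 3 non-hematological toxicity (alopecia, nausea and vomiting excepted).**

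| Grade | Table 0-8, discontinuation | Table 0-8, reduction | Appendix A (diarrhea; other temozolomide-related events) |
|---|---|---|---|
| 3 | yes | yes | reduce one level |
| 4 | yes | no | discontinue |

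Grade 4 is consistent. Grade 3 is not, and the contradiction lies within one row of Table 0-8. Preferring the toxicity rules to the escalation rule does not remove it.

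**Part 2: escalation against reduction.** The plan states no figure to reproduce. Both rules are applied to one hypothetical subject.

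Inputs:
- Dose levels 200, 150 and 100 mg/m²/day (Table 0-9).
- Escalation at ANC ≥1.5 and platelets ≥100 (Sections 4.2 and 8.2).
- Reduction at ANC 0.5 to <1.0 (Table 0-8; Appendix A).
- Blood counts at C1D15 and C2D1 (Section 5.0).

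Subject: ANC 0.8 at C1D15; ANC 1.6 and platelets 120 at C2D1.
1. Section 4.2 with Day 1 counts: 1.6 ≥ 1.5 and 120 ≥ 100, so 200 mg/m².
2. Table 0-8 and Appendix A: 0.5 ≤ 0.8 < 1.0, so one level down once the counts allow resumption. They do, at the same two thresholds.
3. One level down is 100 if counted from the 150 received, or 150 if counted from the planned 200. The protocol does not say which.

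Size for one 5-day course:
- Escalated: 5 × 200 = 1000 mg/m².
- Reduced from 150: 5 × 100 = 500 mg/m²; 1000/500 = 2.0.
- Reduced from the planned 200: 5 × 150 = 750 mg/m²; 1000/750 = 1.33.
- At an illustrative body surface area of 1.8 m²: 360 mg/day against 180 or 270 mg/day.

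Limits of the conflict:
- A Cycle 1 platelet count of 40, or a resolved Grade 3 non-hematological event handled by the reduction cell, gives the same split.
- ANC 1.2 or platelets 80 triggers interruption only, so there is no conflict.
- If the escalation test means nadir counts, 0.8 < 1.5 and escalation is not due. Only non-hematological triggers then conflict. The text does not say when the counts are taken; Day 1 is the natural reading but an assumption.

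**The case against.** The strongest reply is that the escalation question is already answered. Sections 4.2, 4.3 and 8.2 set out the planned regimen, while Table 0-8 and Appendix A are the specific toxicity rules. The Appendix A neutropenia and thrombocytopenia rows deal with exactly this subject: they hold until the resumption threshold is reached and then reduce. Sections 4.4 and 4.4.4 refer dose modification to Appendix A. Temozolomide is given only in the first week of a cycle (Section 4.3.1), so a trigger at Day 15 can act only on the next course; letting escalation win would make the reduction rows pointless.

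Most of this stands. It makes the toxicity rules the ordinary reading and the escalation point a modest one. What remains is that no sentence gives that order of precedence, and the only re-escalation section, 4.4.1, covers cabozantinib alone. The reply does not reach the Table 0-8 overlap. The pointer to Appendix A suggests reduction at Grade 3, but the table still prints the opposite beside it.

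A reader might go further in three ways that the documents do not support:
- That subjects will receive twice the intended dose. This needs Day 1 counts, reduction counted from 150, and an investigator who disregards Appendix A. For a subject already on 200, the escalation sentence has nothing to escalate.
- That 200 mg/m² is itself unsafe. Section 1.3 calls the Cycle 2+ dose standard and FDA-approved.
- That Appendix B is in error because its lowest column is "150 mg/m² (mg daily"). Table 0-9 defines the 100 mg/m² level, and the daily dose is 100 × body surface area.

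**Conclusion.** The temozolomide rules are internally inconsistent as written and should be corrected.

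The Table 0-8 overlap at Grade 3 is a plain contradiction, within the table and with Appendix A. Its consequence for a subject is stopping or continuing temozolomide.

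The missing exception to escalation is a modest safety ambiguity. On a literal reading with Day 1 counts, one course after a Cycle 1 trigger differs 2.0-fold or 1.33-fold, depending on the reference dose. The documents support the absence of a precedence sentence; they do not support a claim that subjects would in practice be dosed wrongly. No trigger rate is given, so no trial-level figure can be stated. The Simon design and its decision limits do not change.

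**What to change.** 1. **Table 0-8.** Make the discontinuation cell of the non-hematological row Grade 4 only, to match Appendix A. If the sponsor prefers to stop at Grade 3, change the reduction cell and the Appendix A Grade 3 lines instead.

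2. **Escalation.** In Sections 4.2, 4.3 and 8.2, and for consistency in the Study Summary and Section 1.3, add: *provided no criterion in Table 0-8 or Appendix A requiring temozolomide reduction or discontinuation has been met in a prior cycle; otherwise Table 0-8 and Appendix A determine the temozolomide dose.*

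   - Confine the clause to temozolomide criteria. Appendix A also lists cabozantinib reductions, for example for hypertension, hand-foot syndrome and proteinuria, and these should not block escalation.
   - Keep the reference to Cycles 2+, so that a subject whose escalation was merely delayed by low Day 1 counts can still escalate later.
   - State when the escalation counts are taken and the reference dose for one level down after Cycle 1.

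**Cost.** One table cell and one clause in five places, by amendment. No added subjects, visits or tests: the C1D15 and C2D1 blood counts are already scheduled. The price is slightly lower temozolomide intensity in subjects with a prior temozolomide trigger, and Grade 3 non-hematological cases continue at a reduced dose rather than stopping.

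A 100 mg/m² column in Appendix B (100 to 250 mg daily for body surface area 1.0 to 2.5 m²) is an optional convenience.
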